10.1.4 SAEs

An SAE is defined as any untoward medical occurrence that at any dose:

1. Results in DEATH.
2. Is LIFE THREATENING.
 - The term "life threatening" refers to an event in which the subject was at risk of death at the time of the event; it does not refer to an event that hypothetically might have caused death if it were more severe.
3. Requires inpatient HOSPITALIZATION or prolongation of existing hospitalization.
4. Results in persistent or significant DISABILITY/INCAPACITY.
5. Is a CONGENITAL ANOMALY/BIRTH DEFECT.
6. Is an IMPORTANT MEDICAL EVENT that satisfies any of the following:
 - May require intervention to prevent items 1 through 5 above.
 - May expose the subject to danger, even though the event is not immediately life threatening or fatal or does not result in hospitalization.
 - Includes any event or synonym described in the Takeda Medically Significant AE List ([Table 10.a](#)).

Table 10.a Takeda Medically Significant AE List

	Term
Acute respiratory failure/acute respiratory distress syndrome	Hepatic necrosis
Torsade de pointes/ventricular fibrillation/ventricular tachycardia	Acute liver failure Anaphylactic shock
Malignant hypertension	Acute renal failure
Convulsive seizure	Pulmonary hypertension
Agranulocytosis	Pulmonary fibrosis
Aplastic anemia	Confirmed or suspected endotoxin shock
Toxic epidermal necrolysis/Stevens-Johnson syndrome	Confirmed or suspected transmission of infectious agent by a medicinal product Neuroleptic malignant syndrome/malignant hyperthermia Spontaneous abortion/stillbirth and fetal death

PTEs that fulfill 1 or more of the serious criteria above are also to be considered SAEs and should be reported and followed up in the same manner (see Sections 10.2.2 and 10.3).

10.1.5 Severity of PTEs and AEs

The different categories of intensity (severity) are characterized as follows:

- Mild: The event is transient and easily tolerated by the subject.
Moderate: The event causes the subject discomfort and interrupts the subject's usual activities.
Severe: The event causes considerable interference with the subject's usual activities.

10.1.6 Causality of AEs

The relationship of each AE to study drug(s) will be assessed using the following categories:

- Related: An AE that follows a reasonable temporal sequence from administration of a drug (including the course after withdrawal of the drug), or for which possible involvement of the drug cannot be ruled out, although factors other than the drug, such as underlying diseases, complications, concomitant drugs and concurrent treatments, may also be responsible.
Not Related: An AE that does not follow a reasonable temporal sequence from administration of a drug and/or that can reasonably be explained by other factors, such as underlying diseases, complications, concomitant drugs, and concurrent treatments.

10.1.7 Relationship to Study Procedures

Relationship (causality) to study procedures should be determined for all PTEs and AEs.

The relationship should be assessed as Related if the investigator considers that there is reasonable possibility that an event is due to a study procedure. Otherwise, the relationship should be assessed as Not Related.

10.1.8 Start Date

The start date of the AE/PTE is the date that the first signs/symptoms were noted by the subject and/or physician.

10.1.9 Stop Date

The stop date of the AE/PTE is the date at which the subject recovered, the event resolved but with sequelae or the subject died.

10.1.10 Frequency

Episodic AEs/PTE (eg, vomiting) or those which occur repeatedly over a period of consecutive days are intermittent. All other events are continuous.

10.1.11 Action Concerning Study Drug

- Drug withdrawn – a study drug is stopped due to the particular AE.
- Dose not changed – the particular AE did not require stopping a study drug.
- Unknown – only to be used if it has not been possible to determine what action has been taken.
- Not Applicable – a study drug was stopped for a reason other than the particular AE eg, the study has been terminated, the subject died for reasons other than the event, dosing with study drug was already stopped before the onset of the AE.

10.1.12 Outcome

- Recovered/resolved – subject returned to first assessment status with respect to the AE/PTE.
- Recovering/resolving – the intensity is lowered by one or more stages: the diagnosis or signs/symptoms has almost disappeared; the abnormal laboratory value improved, but has not returned to the normal range or to Baseline; the subject died from a cause other than the particular AE/PTE with the condition remaining “recovering/resolving”.
- Not recovered/not resolved – there is no change in the diagnosis, signs or symptoms; the intensity of the diagnosis, signs/ symptoms or laboratory value on the last day of the observed study period has got worse than when it started; is an irreversible congenital anomaly; the subject died from another cause with the particular AE/PTE state remaining “Not recovered/not resolved”.
- Resolved with sequelae – the subject recovered from an acute AE/PTE but was left with permanent/significant impairment (eg, recovered from a cardiovascular accident but with some persisting paresis).
- Fatal – the AEs/PTEs which are considered as the cause of death.
- Unknown – the course of the AE/PTE cannot be followed up due to hospital change or residence change at the end of the subject’s participation in the study.

10.2 Procedures

10.2.1 Collection and Reporting of AEs

10.2.1.1 PTE and AE Collection Period

Collection of PTEs will commence from the time the subject signs the informed consent to participate in the study and continue until the subject is first administered study drug (TAK-071) (Day 1 for Cohorts 1 to 9, 13 to 15, and 17 to 22; Day -21 for Cohorts 10 to 12; and Day 1 [if on stable 10 mg dose at Screening] or Day -21 [if donepezil dose increased to 10 mg in subjects already on donepezil 5 mg], or Day -49 [if donepezil initiated as 5 mg dose]) or until screen failure. For subjects who discontinue prior to study drug administration, PTEs are collected until the subject discontinues study participation.

Collection of AEs will commence from the time that the subject is first administered study drug (Day 1 for Cohorts 1 to 9, 13 to 15, and 17 to 22; Day -21 for Cohorts 10 to 12; and Day 1, Day -21, or Day -49 as the case may be [see above]). Routine collection of AEs will continue until the Follow-up Telephone Call/Visit (Day 12 for Cohorts 1 to 6 and 18 to 21, Day 32 for Cohorts 7 to 8 and 10 to 12, Day 39 for Cohorts 9 and 13 to 15, Day 72 for Cohort 16, and Day 28 for Cohort 17).

For subjects in Cohort 16 who receive donepezil during the run-in period, they will be followed-up for PTEs/AEs via weekly phone calls during the run-in period.

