The safety and tolerability of donepezil alone will be evaluated during the donepezil dosing phase (before TAK-071 is given in Cohorts 10 to 12) during the 3-week pretreatment period, and the safety and tolerability of donepezil in combination with TAK-071 (Cohorts 20 to 22) will be evaluated by assessing AEs, clinical laboratory results, physical examination findings, ECG findings, bowel function, and vital signs.

In addition to safety monitoring, TAK-071 plasma and urine PK profiles will be generated and PK parameters derived. It is planned that CSF samples for PK analysis will be obtained in Cohort 3 (following a single dose) and Cohort 9 (at steady-state). CCI [REDACTED]

Approximately 186 subjects are expected to be randomized in this study.

End of study is defined as the date of last visit of the last subject for last clinical assessment.

The treatment groups and cohorts are outlined in [Table 6.a](#).

Table 6.a Overview of Treatment Cohorts

Group	Cohort	Age (years)	Type	Regimen	Number of Subjects per Cohort		Total
					TAK-071	Placebo	
SRD (a)	1 to 6, 18, and 19	18-55	HV	Single	6	2	64
SRD + donepezil post TAK-071 treatment (a, b)	20 to 22	18-55	HV	Single	6	3 (+3 donepezil)	36
MRD (a)	7, 8	18-55	HV	1 dose QD for 21 days	6	2	16
MRD (a)	9	18-55	HV	1 single dose, 7-day washout, 1 dose QD for 21 days	6	2	8
MRD + donepezil pretreatment (a, c)	10 to 12	18-55	HV	1 dose QD for 21 days	6	2	24
MRD	13 to 15	20-55	jHV	1 single dose, 7-day washout, 1 dose QD for 21 days	5	1	18
Subjects with MCI or mild AD (a)	16	55-90	MCI or mild AD (d)	21 days TAK-071 QD (Treatment A) or 21 days of matching placebo (Treatment B). Subjects will be randomized to 2 sequences (AB or BA), with 21 days washout between treatment sequences.	NA	NA	up to 8 (minimum of 6)
Relative BA and FE (e)	17	18-55	HV	Single dose in each of 3 periods with washout period of 21 days after Periods 1 and 2	12	NA	12
Total:							186

jHV=Japanese healthy volunteers, FE=food effect, HV=healthy volunteers, NA=not applicable.

(a) Non-Japanese subjects.

(b) Donepezil (10 mg) will be given as a single dose as an over-encapsulated oral tablet, 24 hours post TAK-071 dose.

[figure not shown]
(c) Donepezil (5 mg QD) will be given as an oral tablet daily for 3 weeks prior to dosing and during the TAK-071 dosing interval.

(d) Subjects with MCI or mild AD (non-Japanese) who have been stable on 10 mg donepezil treatment for at least 21 days or who consent to donepezil run-in period.

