Days -60 to -2	Days -49 to -1	Day -1	Days 1 to 21	Day 22		Day 41	Days 42 to 62	Day 63	Day 73 (±2)
←—Intermittent Confinement—→ Confinement on Days -1 to 2, 11, 20 to 22, 41 to 43, 52, and 61 to 63									

(a) Subjects with MCI or mild AD on stable donepezil (10 mg) treatment or who consent to a donepezil run-in period of 5 mg dose for 28 days and titrate up to 10 mg for at least 21 days. Subjects with previous MCI/AD diagnosis who have been treated with 5 mg for at least 28 days prior to Screening may consent to a donepezil run-in period of 10 mg for at least 21 days.

Figure 6.g Schematic Study Design for Cohort 17

Pretreatment Period		Treatment Periods 1, 2, and 3 (a)		Final Visit	Follow-Up
Screening	Check-in	Single Dose/PK	PK		Follow-up Telephone Call
Days -28 to -2	Day -1	Day 1	Days 2 to 5 and 8	Day 8 Period 3	Day 12 (±2) Period 3
		Washout (b) Days 2 to 21 of Periods 1 and 2 only			
	← Intermittent Confinement →				
	Confinement on Days -1 to 4 and outpatient PK visit on Day 8				

(a) Visit Day count shown as relative to Day 1 of each treatment period.

(b) The total washout period will be 21 days from the time of dosing.

For Cohorts 7 to 8 and 10 to 12, the dosing duration and for Cohorts 9 and 13 to 16, the dosing and/or washout duration may be adjusted if PK data from the SRD part indicate that a different period may be more appropriate (ie, 5 times the observed $t_{1/2z}$). For Cohort 17, washout period may be adjusted if PK data from previous cohorts warrants so.

The planned duration of dosing in all MRD cohorts will be of 21 days. If warranted based on emerging PK data (ie, based on the observed range of $t_{1/2z}$ values) and assuming acceptable safety and tolerability in preceding cohorts, the duration of TAK-071 dosing may be reduced to at a minimum of 14 days or extended for up to a maximum of 28 days.

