9.3.3 Treatment Phase/Washout Phase

For Cohorts 1 to 6 and 18 to 22, the Treatment Phase will consist of a single dose of study drug (for Cohorts 20 to 22 donepezil will be administered approximately 24 hours after the TAK-071 dose). For Cohorts 7, 8, and 10 to 12, the Treatment Phase will consist of 21 QD doses of study drug. For

Cohorts 9 and 13 to 15, the Treatment Phase will consist of a single dose of study drug, followed by a washout period of 7 days and 21 QD doses of study drug.

For Cohorts 9 and 13 to 15, the washout and/or dosing duration may be adjusted with additional day(s) if PK data from the SRD part indicate that a longer duration may be more appropriate.

For Cohort 16 the treatment duration will consist of 21 QD doses of Treatment A (TAK-071) or B (placebo) in Period 1, a 21-day washout, and then 21 daily doses of Treatment A or B in Period 2. Treatment assignments will be switched between Period 1 and 2. A donepezil run-in period of 49 days, prior to starting Treatment A, may be included if the subject is diagnosed at Screening.

For Cohort 17, the treatment duration will consist of a single dose of study drug in each of 3 periods. Washout period of 21 days will follow Periods 1 and 2.

The washout and/or dosing duration may be adjusted with additional day(s) if PK data from the SRD part indicate that a longer washout may be more appropriate.

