9.3.6 Follow-up Visit/Telephone Call

The Follow-up Visit will occur by phone on Day 12 (± 2 days) for Cohorts 1 to 6 and 18 to 22; Day 32 (± 2 days) for Cohorts 7, 8, and 10 to 12; Day 39 (± 2 days) for Cohorts 9 and 13 to 15; Day 73 (± 2 days) for Cohort 16; and Day 12 (± 2 days) of Period 3 for Cohort 17 and will be considered the subject's last visit unless abnormal clinically significant findings are observed at discharge. If abnormal clinically significant findings are observed, subjects must visit the clinic for re-evaluation per investigator's discretion. If no abnormal clinically significant findings are observed, follow-up will occur via a telephone call.

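### Protocol Section 10.2.1.1 dates the end of Cohort 17 adverse event collection as Day 28, which contradicts the Period 3 follow-up call (about study Day 54)

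*Protocol*

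**What the plan says.** Protocol Section 10.2.1.1 states the general rule "Routine collection of AEs will continue until the Follow-up Telephone Call/Visit" and then lists a day for each group of cohorts in parentheses. The end of that list is "Day 72 for Cohort 16, and Day 28 for Cohort 17", with no period named. The same list gives Day 12 for Cohorts 1 to 6 and 18 to 21. The preceding sentences start AE collection at the first administration of study drug, which is Day 1 for Cohort 17, and they include Cohort 22.

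Section 9.3.6 dates the follow-up contact itself. For Cohort 17 it is "Day 12 (± 2 days) of Period 3 for Cohort 17"; for Cohort 16 it is Day 73 (±2); Cohorts 18 to 22 are at Day 12 (±2). Figure 6.g and the Cohort 17 schedule in Appendix A give the same Cohort 17 date. Appendix A also marks AE assessment across the three periods, at the final visit and at follow-up.

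On spacing, Table 6.a describes Cohort 17 as "Single dose in each of 3 periods with washout period of 21 days after Periods 1 and 2", and the notes to Figure 6.g add "The total washout period will be 21 days from the time of dosing" and "Visit Day count shown as relative to Day 1 of each treatment period".

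**The concern.** The protocol gives two different end dates for AE collection in Cohort 17, and the wrong one sits in the section that defines the collection period. The percentage of subjects with at least one treatment-emergent adverse event (TEAE) is a primary safety endpoint (Protocol Section 5.2.1.1), and SAP Section 7.12.1 tabulates TEAEs for Cohort 17. If the stated day were applied from first dose, collection would stop before the third dose is given.

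The same boundary governs SAE reporting. Section 10.2.2 requires SAEs that occur through the AE collection period to be reported under its 24-hour procedure. After that period, only SAEs that are spontaneously reported and considered related to study participation need go to the sponsor. A wrong end day therefore blurs that duty too.

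**Working it through.** **Inputs**
- Dose-to-dose interval: 21 days (Figure 6.g note; Section 9.3.3).
- Cohort 17 size: 12 subjects, 4 per sequence, 3 single doses each (Sections 6.1.4 and 13.3).
- Follow-up: Day 12 (±2) of Period 3 (Section 9.3.6).
- Screening: within 28 days (Section 9.3.1).
- Stated period of evaluation: about 82 days (Section 2.0).

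**Reproducing the plan's own figure**
- Day 1 of Period k = 1 + 21 × (k − 1), which gives study Days 1, 22 and 43.
- Follow-up = 43 + 12 − 1 = study Day 54 (52 to 56 with ±2).
- Screening plus on-study days = 28 + 54 = 82, equal to the stated figure. The calendar is therefore the one the sponsor had in mind.

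**Reading 1: Day 28 counted from first dose.** The start rule in the same section points this way, since collection begins at the first dose and no period is named for the end.
- Position: 28 − 22 + 1 = Day 7 of Period 2.
- Gap to the Period 3 dose: 43 − 28 = 15 days.
- Gap to follow-up: 54 − 28 = 26 days.
- Days uncovered: Days 29 to 42 (14 days of Period 2) plus Days 43 to 54 (12 days of Period 3) = 26 of 54.
- Administrations uncovered: 12 of 12 × 3 = 36, or one third of the cohort's doses.

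**Reading 2: Day 28 counted within a period**, as Figure 6.g counts days. Periods 1 and 2 are only 21 days long, so this could only be Period 3.
- Position: 43 + 28 − 1 = study Day 70.
- This is 70 − 54 = 16 days after the planned last contact, so nothing would be missed.

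Neither reading coincides with the follow-up call on Day 54.

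**Balance across regimens under Reading 1.** Table 6.b uses sequences ABC, BCA and CAB with 4 subjects each, so every regimen occurs 4 times in each period. A Day 28 cutoff would leave each regimen with 4 fully covered, 4 truncated and 4 uncovered administrations.

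**Scale against the whole study.** Planned TAK-071 or placebo administrations, assuming 8 subjects in Cohort 16 and not counting donepezil:

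| Cohorts | Administrations |
|---|---|
| 1 to 6, 18, 19 | 64 |
| 20 to 22 | 36 |
| 7, 8 | 16 × 21 = 336 |
| 9 | 8 × 22 = 176 |
| 10 to 12 | 24 × 21 = 504 |
| 13 to 15 | 18 × 22 = 396 |
| 16 | 8 × 42 = 336 |
| 17 | 36 |
| Total | 1,884 |

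12 / 1,884 is about 0.6%.

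**Other entries in the list.** Cohort 16 is given Day 72 against Day 73 (±2), that is Days 71 to 75, so the stated day lies inside the window. Cohort 22 is absent from the end list but present in the start rule and in Section 9.3.6.

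**The case against.** The strongest reply is that Section 10.2.1.1 ends collection at an event, the follow-up call, and that the days in parentheses only restate when the call occurs. Section 9.3.6 dates that call correctly. Appendix A schedules AE assessment in all three periods and at follow-up, and its footnote captures any event after the first Period 1 dose. Section 10.2.1.2 also requires AEs to be assessed at each study visit. A site would have to set all of this aside to stop at Day 28. This stands, and it is why loss of data cannot be asserted.

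A reader might infer that the primary TEAE endpoint will miss a third of the doses given. The documents do not support that. The loss depends on the parenthetical day overriding the call and Appendix A, it depends on counting from first dose, and the third is of Cohort 17 only. A reader might also infer that regimens would be compared on unequal observation. The balanced sequences rule that out as planned.

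The reply does not dispose of the discrepancy. Day 28 fits the follow-up date on neither count. The SAP's window of 30 days after the last dose is an analysis rule and cannot recover events that were never collected. Section 7.4.2 already cites preliminary Cohort 17 food-effect results, which suggests that much of that cohort's dosing was done by this amendment. That limits what a text change can achieve for Cohort 17, and it makes checking what was actually collected more useful.

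**Conclusion.** The point holds as an internal contradiction that should be reconciled. The end day for Cohort 17 in Section 10.2.1.1 is wrong against Section 9.3.6, Figure 6.g and Appendix A, and it sits in the rule that bounds both AE collection and mandatory SAE reporting. On the more natural count it falls 15 days before the Period 3 dose and 26 days before follow-up, which would put at risk 12 of Cohort 17's 36 administrations. This rests on the planned 21-day spacing, 12 subjects completing three periods, and someone applying the stated day in place of the call. Data loss is possible but not demonstrated. The Cohort 16 and Cohort 22 entries are minor; they suggest that the list was not updated together with Section 9.3.6.

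**What to change.** Reconcile the list of days in Section 10.2.1.1 with Section 9.3.6 and Appendix A: Cohort 17, Day 12 (±2) of Period 3; Cohorts 18 to 22, Day 12; Cohort 16, Day 73. Alternatively, delete the list and refer to Section 9.3.6. The sponsor should also confirm, and state in the study report, that Cohort 17 AEs and SAEs were collected through the Period 3 follow-up contact. The cost is one sentence and one data check. The visits already exist, and no treatment or procedure changes.

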10.2.1.2 PTE and AE Reporting

At each study visit, the investigator will assess whether any subjective AEs have occurred. A neutral question, such as “How have you been feeling since your last visit?” may be asked. Subjects may report AEs occurring at any other time during the study. Subjects experiencing a serious PTE must be monitored until the symptoms subside and any clinically relevant changes in laboratory values have returned to Baseline or there is a satisfactory explanation for the change. Nonserious PTEs, related or unrelated to the study procedure, need not to be followed-up for the purposes of the protocol.

All subjects experiencing AEs, whether considered associated with the use of the study drug or not, must be monitored until the symptoms subside and any clinically relevant changes in laboratory values have returned to Baseline or until there is a satisfactory explanation for the changes observed. All PTEs and AEs will be documented in the PTE/AE page of the eCRF, whether or not the investigator concludes that the event is related to the drug treatment. The following information will be documented for each event:

1. Event term.
2. Start and stop date and time.
3. Frequency.
4. Severity.

5. Investigator's opinion of the causal relationship between the event and administration of study drug(s) (related or not related) (not completed for PTEs).
6. Investigator's opinion of the causal relationship to study procedure(s), including the details of the suspected procedure.
7. Action concerning study drug (not applicable for PTEs).
8. Outcome of event.
9. Seriousness.

10.2.2 Collection and Reporting of SAEs

When an SAE occurs through the AE collection period it should be reported according to the following procedure:

A Takeda SAE form (eCRF SAE form in electronic data capture [EDC]) must be completed, in English and signed by the investigator immediately or within 24 hours of first onset or notification of the event. A paper SAE form should only be used if EDC is not available. The information should be completed as fully as possible but contain, at a minimum:

- A short description of the event and the reason why the event is categorized as serious.
- Subject identification number.
- Investigator's name.
- Name of the study drug(s).
- Causality assessment.

The SAE form should be transmitted within 24 hours to the attention of the contact listed in Section 1.0.

Any SAE spontaneously reported to the investigator following the AE collection period should be reported to the sponsor if considered related to study participation.

Reporting of serious PTEs will follow the procedure described for SAEs.

10.2.3 Reporting of Abnormal Liver Function Tests

If a subject is noted to have ALT or AST elevated $>3 \times \text{ULN}$ on 2 consecutive occasions, the abnormality should be recorded as an AE. In addition, an LFT Increases eCRF must be completed providing additional information on relevant recent history, risk factors, clinical signs and symptoms and results of any additional diagnostic tests performed.

If a subject is noted to have ALT or AST $>3 \times \text{ULN}$ and total bilirubin $>2 \times \text{ULN}$ for which an alternative etiology has not been identified, the event should be recorded as an SAE and reported as per Section 10.2.2. The investigator must contact the Medical Monitor for discussion of the relevant subject details and possible alternative etiologies, such as acute viral hepatitis A or B or other acute liver disease or medical history/concurrent medical conditions. Follow-up laboratory

tests as described in Section 9.1.9 must also be performed. In addition, an LFT Increases eCRF must be completed and transmitted with the Takeda SAE form (as per Section 10.2.2).

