6.3 Premature Termination or Suspension of Study or Investigational Site

6.3.1 Criteria for Premature Termination or Suspension of the Study

The study will be completed as planned unless one or more of the following criteria are satisfied that require temporary suspension or early termination of the study.

- New information or other evaluation regarding the safety or efficacy of the study drug that indicates a change in the known risk/benefit profile for the product, such that the risk is no longer acceptable for subjects participating in the study.
 - Significant violation of Good Clinical Practice (GCP) that compromises the ability to achieve the primary study objectives or compromises subject safety.
 - Study-specific criteria for terminating the study (eg, study meets predefined rule for futility or benefit, study meets predefined stopping rules within or between cohorts per Section 6.1.5).
 1. Dose escalation will be stopped if it is predicted that further dose escalation will not result in a further increase in plasma exposure (ie, an exposure ceiling is reached).
 2. Dose escalation will be stopped at a dose level (ie, 1 escalation step) below the dose that is predicted to give a TAK-071 AUC or C_{max} that exceeds that of the 28-day monkey toxicology study NOAEL.
 3. Two or more subjects in any single cohort or across more than 1 cohort experience any of the Takeda Medically Significant List events (as outlined in Table 10.a).*
 4. Two or more subjects in any single cohort or across more than 1 cohort experience alanine aminotransferase (ALT) and/or aspartate aminotransferase (AST) elevations $>5\times$ upper limit of normal (ULN) in the absence of a concomitant bilirubin increase [see point 5 below].*
 5. One or more subjects in any single cohort or across more than 1 cohort experience ALT and/or AST elevations $>3\times$ ULN in the presence of a total bilirubin increase $>2\times$ ULN or an international normalized ratio (INR) >1.5 without findings of cholestasis or other alternate etiology to explain the elevations (ie, “Hy’s Law cases”).
 6. Two or more subjects in any single cohort or across more than 1 cohort experience ALT and/or AST elevations $>3\times$ ULN with the appearance of fatigue, nausea, vomiting, right upper quadrant pain or tenderness, fever, rash, and/or eosinophilia ($>5\%$).*

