7.5 Criteria for Discontinuation or Withdrawal of a Subject

The primary reason for discontinuation or withdrawal of a subject from the study or study drug should be recorded in the eCRF using the following categories. For screen failure subjects, refer to [Section 9.1.19](#).

1. Pretreatment event (PTE) or AE. The subject has experienced a PTE or AE that requires early termination because continued participation imposes an unacceptable risk to the subject's health or the subject is unwilling to continue because of the PTE or AE.
 - Liver function test (LFT) abnormalities
Study medication should be discontinued immediately with appropriate clinical follow-up (including repeat laboratory tests, until a subject's laboratory profile has returned to normal/Baseline status, see [Section 9.1.9](#)), if any 1 of the following circumstances occur at any time during study drug treatment:
 - ALT or AST $>8 \times$ ULN.
 - ALT or AST $>5 \times$ ULN and persists for more than 2 weeks.
 - ALT or AST $>3 \times$ ULN in conjunction with elevated total bilirubin $>2 \times$ ULN or INR >1.5 .
 - ALT or AST $>3 \times$ ULN with appearance of fatigue, nausea, vomiting, right upper quadrant pain or tenderness, fever, rash and/or eosinophilia ($>5\%$).

2. Significant protocol deviation. The discovery postrandomization that the subject failed to meet protocol entry criteria or did not adhere to protocol requirements, and continued participation poses an unacceptable risk to the subject's health.
3. Lost to follow-up. The subject did not return to the clinic, and attempts to contact the subject were unsuccessful. Attempts to contact the subject must be documented.
4. Voluntary withdrawal. The subject (or subject's legally acceptable representative) wishes to withdraw from the study. The reason for withdrawal, if provided, should be recorded in the eCRF.

Note: All attempts should be made to determine the underlying reason for the withdrawal and, where possible, the primary underlying reason should be recorded. Withdrawal due to an AE should not be recorded in the "voluntary withdrawal" category.

5. Study termination. The sponsor, IRB, or regulatory agency terminates the study.
6. If, in spite of preventive measures, the PK exposure (C_{max} and AUC_{24} for steady-state) in an individual unexpectedly exceeds, or is predicted to exceed upon repeat dosing, the corresponding average steady-state exposure at the NOAEL in the 28-day monkey toxicology study.
7. Other.

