The local laboratory will perform laboratory tests for hematology, coagulation, serum chemistries, and urinalysis. The results of laboratory tests will be returned to the investigator, who is responsible for reviewing and filing these results.

If subjects experience ALT or AST >3×ULN, follow-up laboratory tests (at a minimum, serum alkaline phosphatase, ALT, AST, total bilirubin, γ -glutamyl transferase, and INR) should be performed within a maximum of 7 days and preferably within 48 to 72 hours after the abnormality was noted.

If the ALT or AST remains elevated $>3\times$ ULN on these 2 consecutive occasions, the investigator must contact the Medical Monitor for consideration of additional testing, close monitoring, possible discontinuation of study drug, discussion of the relevant subject details and possible alternative etiologies. The abnormality should be recorded as an AE (please refer to Section 10.2.3 Reporting of Abnormal Liver Function Tests for reporting requirements).

Please refer to Section 7.5 for discontinuation criteria and Section 10.2.3 for the appropriate guidance on Reporting of Abnormal Liver Function Tests in relation to ALT or AST $>3\times$ ULN in conjunction with total bilirubin $>2\times$ ULN.

Laboratory reports must be signed and dated by the principal investigator or subinvestigator indicating that the report has been reviewed and any abnormalities have been assessed for clinical significance. Any abnormalities identified prior to first dose will require clear and complete documentation in the source documents as to the investigator's assessment of not clinically significant before proceeding with enrollment/randomization.

All clinically significant laboratory abnormalities must be recorded as a PTE/AE in the subject's source documents and on the appropriate eCRF. A clinically significant laboratory abnormality that has been verified by retesting will be followed until the abnormality returns to an acceptable level or a satisfactory explanation has been obtained.

The investigator will maintain a copy of the laboratory accreditation and the reference ranges for the laboratory used.

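### The liver-signal SAE rule in Protocol 10.2.3 omits the INR alternative that one-subject stopping rule 5 (6.3.1) and the drug-stop criterion (7.5) both accept

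*Protocol*

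**What the plan says.** **Reporting.** Protocol 10.2.3 has two tiers. ALT or AST >3×ULN on two consecutive occasions is an AE with an LFT Increases eCRF. The upper tier adds total bilirubin >2×ULN to a single such elevation, and its wording is: "for which an alternative etiology has not been identified, the event should be recorded as an SAE and reported as per Section 10.2.2". Contact with the Medical Monitor is also required at this tier. Section 10.2.2 sets 24 hours for that report. INR is not mentioned in 10.2.3.

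**Study stopping.** Rule 5 of Protocol 6.3.1 is met when "One or more subjects in any single cohort or across more than 1 cohort experience ALT and/or AST elevations" beyond 3×ULN and a second criterion also holds. That criterion is bilirubin >2×ULN or its stated alternative, "or an international normalized ratio (INR") above 1.5. The case must also be one "without findings of cholestasis or other alternate etiology to explain the elevations". The rule calls these Hy's Law cases.

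**Subject stopping.** Protocol 7.5 uses the same bilirubin-or-INR pair, without an etiology qualifier: "Study medication should be discontinued immediately with appropriate clinical follow-up".

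**Laboratory follow-up.** Protocol 9.1.9 requires a retest after any ALT or AST >3×ULN, and the wording on the panel and its timing ends: "transferase, and INR) should be performed within a maximum of 7 days and preferably within 48 to 72 hours". It also says "All clinically significant laboratory abnormalities must be recorded as a PTE/AE". Its cross-reference reads "Please refer to Section 7.5 for discontinuation criteria and Section 10.2.3 for the appropriate guidance on Reporting of Abnormal Liver Function Tests" and then names the bilirubin combination only.

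**The concern.** In rule 5, bilirubin and INR are alternatives in one sentence, under one label and with one threshold of a single subject. The reporting section takes up only the first. A subject with unexplained ALT or AST >3×ULN, INR >1.5 and bilirubin ≤2×ULN therefore meets a study-stopping rule, while 10.2.3 mandates no SAE report.

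A rule that one subject can trigger works only if the sponsor hears of that subject promptly. The study is first-in-human and has no data monitoring committee (Protocol 11.0). The sponsor–investigator review in 11.0 takes place before an additional cohort is dosed, so it sets no time for a case arising inside a running 21-day cohort.

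**Working it through.** The plan states no figure on this point, so the check is a comparison of criteria.

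**Inputs**
- A = ALT or AST >3×ULN (6.3.1, 7.5, 10.2.3)
- B = total bilirubin >2×ULN (6.3.1, 7.5, 10.2.3)
- I = INR >1.5 (6.3.1, 7.5)
- E = another etiology found (6.3.1, 10.2.3). Rule 5 names cholestasis separately; here it is assumed to count as another etiology.

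**Criteria**
- Rule 5: A and (B or I) and not E
- 7.5 drug stop: A and (B or I)
- 10.2.3 SAE: A and B and not E

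**Given A and not E**

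| Bilirubin >2×ULN | INR >1.5 | Rule 5 | 7.5 | 10.2.3 SAE |
|---|---|---|---|---|
| no | no | no | no | no |
| no | yes | **yes** | **yes** | **no** |
| yes | no | yes | yes | yes |
| yes | yes | yes | yes | yes |

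Rule 5 is met in 3 of 4 combinations and the SAE mandate in 2 of 4, so they differ in 3 − 2 = 1.

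**All 2⁴ = 16 combinations of A, B, I and E, compared with rule 5**
- Current 10.2.3: 1 of 16 disagrees.
- A and (B or I) and not E: 0 of 16 disagree.
- Unbracketed wording read as [(A and B) or I] and not E: 2 of 16 disagree. Both have INR >1.5 without ALT or AST >3×ULN. The brackets therefore matter.

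**Subjects needed for the hepatic rules in 6.3.1.** Rule 4: two or more. Rule 5: one or more. Rule 6: two or more. So 1 of 3 is met by a single subject.

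**What already applies to the differing combination**

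| Provision | When it applies | Time set for telling the sponsor |
|---|---|---|
| Drug stop (7.5) | at once | none |
| Retest including INR (9.1.9) | within 7 days, preferably 48 to 72 hours | none |
| Medical Monitor contact (9.1.9) | ALT or AST still >3×ULN on two consecutive occasions, whatever the bilirubin | none for the contact |
| AE record (9.1.9) | clinically significant abnormality | none |
| LFT Increases eCRF (10.2.3) | two consecutive elevations | none |
| Consider discontinuing cohort entry (6.1.5) | onset of an AE whose relation to drug cannot be denied and which makes continued dosing difficult | none |
| SAE (10.1.4, Table 10.a) | investigator considers it an important medical event, or diagnoses acute liver failure or hepatic necrosis | 24 hours (10.2.2) |

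Only the last row carries a clock. For this combination it depends on the investigator's discretion or a listed diagnosis, not on a laboratory threshold.

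**The case against.** The strongest reply is that the protocol already escalates this case. The subject is taken off drug immediately. Medical Monitor contact under 9.1.9 does not depend on bilirubin. If INR >1.5 first appears on the retest and ALT or AST is still >3×ULN, that duty arises from the same result. The cohort-entry criterion in 6.1.5 works from onset, not from the between-cohort review. A case that progresses to acute liver failure or hepatic necrosis is an SAE by list. Stopping rules and SAE definitions also serve different purposes, and nothing in the documents says that 10.2.3 must mirror rule 5.

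Most of this stands, and it rules out several stronger readings. A reader might infer that such a subject would stay on drug, or that the sponsor need never be told; 7.5 and 9.1.9 contradict both. A reader might infer that every stopping trigger ought to be an SAE. The protocol does not work that way: rules 4 and 6 and other 7.5 criteria are not automatic SAEs either.

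What the reply leaves open is narrow. The mandatory contact needs a second elevation and has no deadline, and the SAE route is not automatic. For the bilirubin alternative of the same rule, the 24-hour report is automatic, and the protocol gives no reason for the difference.

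**Conclusion.** The mismatch holds in limited form. For one of the two alternatives in a one-subject stopping rule, no SAE report with a 24-hour clock is mandated on first detection. The size is one logical combination: 1 of 4 among unexplained transaminase elevations.

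That count carries no frequencies. The documents support no claim about how often such a case would occur, how long notice would be delayed, or how many further doses would be given. The result assumes that cholestasis counts as another etiology.

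Minor. No endpoint or planned analysis is affected: the primary safety endpoints count TEAEs and markedly abnormal values whether or not an event is serious. It is a low-cost wording improvement.

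**What to change.** In Protocol 10.2.3, second paragraph, replace the laboratory condition with: *ALT or AST >3×ULN and either (a) total bilirubin >2×ULN or (b) INR >1.5*. Keep the existing etiology qualifier, adding *(including cholestasis)* after the word etiology. The (a)/(b) form prevents an isolated INR >1.5 from being read as an SAE. As an editorial match, add the INR alternative to the 9.1.9 cross-reference.

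No new threshold is needed, because INR >1.5 is already in 6.3.1 and 7.5. No new test is needed: INR is in the 9.1.9 retest panel, and coagulation is in the scheduled laboratory tests. The protocol's Cohort 17 schedule in Appendix A lists no coagulation, so on that schedule INR would come from the retest.

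The cost is an occasional extra SAE. It may carry expedited SUSAR reporting and forwarding to the IRB (10.3.1), and, where relation to drug cannot be denied, it engages the SAE criterion on cohort entry (6.1.5). That is proportionate for a case that already meets a study-stopping rule.
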